1.3.6 Admission procedure

Consistent with usual clinical practice, physical exam including blood pressure check, pelvic examination, urine pregnancy test, cervical cytology evaluation (if not completed within the ASCCP recommended screening interval), and testing for gonorrhea and chlamydia (if indicated based on Centers for Disease Control and Prevention screening algorithms) will be performed at the insertion visit by the primary medical provider. Patients will have access to these results which will be in their primary medical records. Bedside ultrasound may be performed to ensure correct fundal placement of the IUS per provider preference, but this is not routine care and will not be required. Patients will be instructed on how to palpate their IUS strings.

After the medical visit is complete, interested and eligible participants will meet with study staff to complete the informed consent process. Consenting of Spanish-speaking patients will be performed with use of an in-person or phone Spanish interpreter to ensure informed consent. Study forms translated into Spanish will be available. Baseline demographic information will be collected by brief interview, including menstrual history, contraception history, sexual and pregnancy history, BMI/weight, ethnicity, age, and baseline use of panty liners (as advised by Mishell et al to avoid confounding data on bleeding/spotting days) (32). Subjects will receive training on the use of the bleeding diary procedures including the text message/email and paper diaries. Estimated time to complete study procedures during the clinic visit is 20 minutes. For patients who express interest in participating in the study but are unsure of their desire to enroll immediately, there will be the option of returning to the clinic within three days of IUS insertion to complete the enrollment study procedures as described above. Prospective bleeding data will be collected starting on the day of enrollment. Women who enroll after their insertion visit will verbally provide data for bleeding or spotting that occurred after insertion and prior to enrollment.

Between IUS insertion and study visit 1 (occurring 14-21 days after insertion), baseline bleeding with the LNG-IUS will be prospectively collected using bleeding diaries. This data will be used later as a covariate in analysis. A co-investigator (ob/gyn physician) will call each subject after at least 12 days of bleeding data collection to review exclusion criteria and to schedule study visit 1 if appropriate, as described in section 1.3.4. Subjects reporting concerns with their IUS will be referred to their primary provider or scheduled for a triage visit in family planning clinic to be examined by a physician as clinically indicated.

At study visit 1, bleeding diaries will be reviewed, and VAS scales (0-100mm) will be completed to obtain baseline assessment of bleeding satisfaction with the LNG-IUS. Each subject will receive one bottle of their assigned medication. Participants will be instructed to begin use of the study medication on day 21 after the insertion of their LNG-IUS and continue to take a twice daily oral dose of 10 mg for seven days. Estimated time to complete this visit is 15 minutes. Participants will receive a single text message or email reminder on the day they are due to start study medication. There will not be any specimens collected at this visit and there will be no results to share with subjects.

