1.3.3 Criteria for the selection of subjects

Subjects: This study will prospectively enroll English and Spanish speaking women 15-45 years of age seeking initiation of LNG-IUS for contraceptive purposes at the OHSU OB/GYNS clinics. They must have access to a reliable cell phone and must be willing to receive and respond to a daily text or email message to assess bleeding.

Exclusion criteria: Postpartum within six months, pregnant, breast-feeding, LNG-IUS prescribed to treat abnormal uterine bleeding, switching from DMPA, IUS removal and replacement, undiagnosed abnormal uterine bleeding pre-dating placement of IUS, bleeding dyscrasias, anticoagulation use, active cervicitis, allergy to tamoxifen, history of venous thromboembolism, current or past breast or uterine malignancy, use of medication contraindicated with tamoxifen (coumadin, letrozole, bromocriptine, rifampicin, aminoglutethimide, phenobarbital).

Additional exclusions prior to randomization: noncompliance with electronic bleeding diary; clinical evidence of IUD complication (e.g. heavy bleeding suspicious for expulsion (complete or partial); unusual pelvic pain; fever and clinical exam suggesting endometritis.

No vulnerable populations will be specifically recruited or included in this study. Subjects between the ages of 15-18 years of age may be enrolled in this study, but will not be considered a vulnerable population or children since research procedures involve providing birth control information and services.

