1.3.8 Risks and Benefits to Participants

Risks and discomforts

Risks to subjects include experiencing side effects from tamoxifen. The most common side effects reported with long term use are hot flushes (33%), bone pain (6%), gastrointestinal distress (5%), or fatigue (4%) (31). Risks of endometrial pathology including endometrial hyperplasia have been associated with long-term use of tamoxifen, but not with short-term use (31). Other risks of long-term use include increased risk of blood clots and stroke. Among women who developed pulmonary emboli, diagnosis occurred at a mean of 27 months from onset of tamoxifen treatment, with earliest event reported at 2 months of treatment (31). Women

using tamoxifen may be at increased risk for developing ovarian cysts with long-term use, but these resolve after discontinuation of use. Given that participants will only be using tamoxifen for one week in this study, an increase in severe adverse events is not anticipated. In short term use, the most common side effect reported was headache in up to 20% of women.

Women with a contraindication to tamoxifen use will be excluded from this study. This includes pregnant women given concern for teratogenicity. It is not known if tamoxifen is excreted in breast milk, but it has been shown to inhibit lactation. It has also been shown to cause reproductive tract lesions in exposed neonatal rodents (31), thus lactating women will also be excluded. Women regularly taking medications that interact with tamoxifen will also be excluded as described in section 1.3.3.

Other risks to participants include time spent participating in study without guarantee of benefit. It is estimated that daily time spent on participation will be no more than five minutes per day, in addition to the 15-minute study visit and the 5-10 minutes for the completion survey. Despite little time required for participation, this may be seen as an inconvenience to subjects.

There is a small risk of breach of confidentiality with potential risk disclosure of sensitive information including menstrual, sexual, and obstetric histories. Information discussed may be seen by participants as embarrassing or very personal. They will have a right to refuse disclosure of any questions they do not wish to discuss.

Benefits:

Participants may or may not personally benefit from being in this study. There is a possibility the study drug will improve participants' bleeding patterns and satisfaction with their LNG-IUS.

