1.6 Main problems anticipated

Recruitment: The family planning clinic at OHSU provides insertion of approximately 3-5 LNG-IUS devices per week. Additional insertions occur in the resident and generalist clinics. By targeting eligible women at clinic visits and by minimizing follow up procedures, we anticipate that recruitment will be feasible to complete within six months.

Retention: The short duration of the study and minimal follow up procedures should maximize retention. Similar prior studies in the LNG-IUS had low dropout rates, all with <20% loss to follow up (16,26,27). The proposed project is shorter duration (51 days total), which should decrease dropout even further. Nevertheless, our sample size was designed to account for a 20% dropout rate due to this risk of poor retention in women experiencing ongoing bleeding. Details on how we will manage loss to follow up are included in section 1.3.7.

Bleeding diaries: The text or email message bleeding diary through Mir3 has been utilized in similar studies with excellent response rates. However, a portion of participants in older studies had difficulty receiving or responding to text messages due to incompatible cell phone technology. Subjects who have difficulty receiving or responding to daily text messages can opt to receive identical email study survey messages instead and will have a paper diary to use as backup, which will utilize the exact same question and response categories.

Any unanticipated problems will be addressed by the PI and study co-investigators, with changes to the protocol as needed. Unanticipated problems could include medication side

effects or pregnancy in a study subject. Any pregnancy occurring during the study will be considered a serious adverse event and will prompt review of the study protocol and possible study discontinuation of the study.

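### Pregnancy is excluded because of teratogenicity, but no test confirms its absence when the drug is dispensed, 14 to 21 days after the only pregnancy test described

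*Combined protocol and SAP*

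**What the plan says.** **The exclusion and its reason.** Section 1.3.3 lists the general exclusions, which begin "Postpartum within six months, pregnant, breast-feeding, LNG-IUS prescribed to treat abnormal uterine bleeding". Section 1.3.8 explains that women with a contraindication to tamoxifen are kept out, and adds "This includes pregnant women given concern for teratogenicity".

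**The test.** Section 1.3.6 describes usual care at insertion as "physical exam including blood pressure check, pelvic examination, urine pregnancy test, cervical cytology evaluation" and further items, which "will be performed at the insertion visit by the primary medical provider". No other pregnancy test appears in the protocol.

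**What happens before dosing.** Section 1.3.6 sets the baseline diary period as "Between IUS insertion and study visit 1 (occurring 14-21 days after insertion". Section 1.3.4 has the pharmacy randomize each woman the day before that visit. At the visit she receives the full seven-day supply, to start on day 21. Section 1.3.6 states of this visit: "There will not be any specimens collected at this visit and there will be no results to share with subjects".

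**The later check.** A physician co-investigator telephones each woman before visit 1. Section 1.3.6 says that the call reviews exclusion criteria, without limiting which, and refers to section 1.3.4. Section 1.3.4 says that it reviews post-insertion exclusions. Section 1.3.3 introduces the further criteria for that stage with "Additional exclusions prior to randomization: noncompliance with electronic bleeding diary; clinical evidence of IUD complication", and pregnancy is not among them.

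**If pregnancy occurs.** Section 1.3.9 ends the woman's participation and unblinds her medication. Section 1.6 adds: "Any pregnancy occurring during the study will be considered a serious adverse event and will prompt review of the study protocol", with discontinuation of the study as a possible result.

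**The concern.** An exclusion made for fetal safety matters most at the moment of exposure. Here it is tested once, at a clinical visit run independently of the study, and is not tested again before the drug is handed over. A woman who conceived shortly before insertion could test negative on day 0, be pregnant on day 21, and take the assigned drug with every written step followed.

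Two things are at stake. The first is fetal exposure to tamoxifen, which the exclusion is meant to prevent. The second is the conduct of a small trial. Under sections 1.3.9 and 1.6 a pregnancy in either arm ends participation, unblinds one woman, counts as a serious adverse event and opens the question of stopping the study. The protocol sets out the response to a pregnancy but schedules no test that would find one.

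**Working it through.** **Step 1: intervals, from the schedule in sections 1.3.4 and 1.3.6.** Take insertion as day 0.

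| Interval | Arithmetic | Result |
|---|---|---|
| Test to dispensing | 14 − 0 to 21 − 0 | 14 to 21 days |
| Test to first dose | 21 − 0 | 21 days |
| Dispensing to first dose | 21 − 21 to 21 − 14 | 0 to 7 days |
| Test to last dosing day | 21 + 7 − 1 | day 27 |
| Pregnancy tests described after day 0 | count | 0 |

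**Step 2: does the telephone review fill the gap?** The sections set side by side:

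- Section 1.3.6: exclusion criteria are reviewed, without limit. Read alone, this includes pregnancy.
- Section 1.3.4, to which 1.3.6 refers: post-insertion exclusions are reviewed. This is narrower.
- Section 1.3.3: the list for that stage covers diary compliance and IUS complications. It supplements the general list, so pregnancy remains an exclusion, but the text does not say that it is re-checked.

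The scope of the call is therefore ambiguous. On the broadest reading it still collects only what the woman reports. Section 1.1.1 describes bleeding on the LNG-IUS as ranging from amenorrhea to prolonged bleeding, so her bleeding pattern is a weak cue.

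**Step 3: conception after insertion.** Section 1.1.1 gives a first-year failure rate below 1%. If this is spread evenly over the year (an assumption), the risk over 21 days is below 1% × 21/365 = 0.058%. Among 42 women that is fewer than 42 × 0.00058 = 0.024 expected cases. This route is small.

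**Step 4: conception before insertion, missed by the day-0 test.** The failure rate does not cover this, and the documents give no figure. Assume a probability p of 0.2% to 1% per woman, for illustration only. Expected cases = n × p.

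| Group | p = 0.2% | p = 1% |
|---|---|---|
| Tamoxifen arm, n = 21 | 21 × 0.002 = 0.042 | 21 × 0.01 = 0.21 |
| Both arms, n = 42 | 42 × 0.002 = 0.084 | 42 × 0.01 = 0.42 |

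The chance of at least one case in the tamoxifen arm is 1 − (1 − p)^21, which is 1 − 0.998^21 = 4.1% at the lower rate and 1 − 0.99^21 = 19.0% at the upper.

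The tamoxifen arm is the right denominator for drug exposure. Both arms together are right for the trial-level consequences, because a pregnancy on placebo triggers the same rules.

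**Step 5: order of events.** Randomization is on the day before visit 1, so a check made at visit 1 falls after randomization. It can stop a pregnant woman from being dosed, but she is already in the intention-to-treat population set by section 1.3.11.

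**The case against.** The strongest reply is that the plan already has several safeguards. Pregnancy is a standing exclusion, a physician calls every woman before visit 1, and one sentence in section 1.3.6 can be read to include pregnancy in that call. The device itself is highly effective. The consent form was not available for this review and may contain further precautions. All of this stands. It means that the exclusion is not verified by a test, which is less than saying that it is not checked at all.

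Four stronger readings are tempting, and the documents do not support them:

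- **That the call could not detect a pregnancy.** A woman may know or suspect that she is pregnant and say so. The supportable statement is that the call cannot be relied on.
- **That expulsion leaves women pregnant and dosed.** Expulsion is not pregnancy, and clinical evidence of complete or partial expulsion is already an exclusion before randomization. Women are taught to feel for the strings, and those with concerns are referred. What remains is an unrecognised expulsion followed by conception within three weeks, which is a much narrower case.
- **That early-pregnancy bleeding would bias the primary outcome.** With fewer than 0.5 cases expected among 42 women even at the upper assumed rate, and participation ending once a pregnancy is recognised, the effect is negligible.
- **That all 42 women are at risk of drug exposure.** Only 21 are assigned tamoxifen.

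It can also be said that a test at visit 1 is an incomplete remedy: it may be up to 7 days old at first dose, and it follows randomization. Both points are correct. They bear on how the change is made. A check 0 to 7 days before first dose is still much closer to exposure than one 21 days before.

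**Conclusion.** The point holds as a gap in eligibility verification and participant safety. An exclusion justified by teratogenicity has no confirming test at randomization, dispensing or first dose, the sections disagree on what the telephone review covers, and the wording for visit 1 rules out a specimen-based check there.

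The expected number of events is small: 0.04 to 0.21 exposures to tamoxifen, and 0.08 to 0.42 pregnancies across both arms. These figures rest wholly on the assumed 0.2% to 1% for conceptions missed at insertion and would scale in proportion to any other rate. The sample size, the power and the primary comparison are not affected. The change is worth making because the consequence of one event is serious, for the woman and for the trial, and the check is cheap at a visit that is already held.

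**What to change.** 1. Reconcile sections 1.3.3, 1.3.4, 1.3.6 and 1.3.8. Name pregnancy expressly among the exclusions re-checked before randomization, and describe the scope of the telephone review in the same way wherever it appears.
2. State how absence of pregnancy is confirmed before the bottle is handed over. Repeating the urine test already used at insertion is the low-cost option. The method is for the investigators and the IRB to choose.
3. If a test is used, amend the sentence in section 1.3.6 on specimens at visit 1, check the similar statement in section 1.3.10, and align the consent form.
4. Settle the order of events. Either randomize after the check, or state how a woman found pregnant after randomization but before dispensing is handled in the intention-to-treat analysis. Say also whether the unblinding rule in 1.3.9 and the serious-adverse-event rule in 1.6 apply to a woman found pregnant before any dose.

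**Cost.** One urine specimen per woman at visit 1, wording changes to the protocol and consent form, and possibly a change in when the pharmacy randomizes. The check may still be up to 7 days old at first dose, so it narrows the gap without closing it.

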1.3.7 Follow-up procedure

Bleeding diaries

The primary outcome variable of this study is the total number of bleeding/spotting days over 30 days, but other bleeding outcomes including duration of bleeding-free episodes and frequency of bleeding episodes will be assessed as secondary outcomes. In order to collect bleeding data, all subjects will be asked to complete both paper and electronic bleeding diaries. For the electronic bleeding diary, after initial enrollment, participants will start receiving a daily text or email message from a study-affiliated messaging service (developed with Mir3, San Diego, CA) prompting a response about their bleeding for the day. Subjects can indicate at enrollment whether they want to receive the message via text or email. This approach using the

same service provider has been previously used by our group and others with excellent real-time response rates (>90%) (33). The text message/email bleeding diary for this project was uniquely designed by OHSU and Mir3 to fit the needs of this study. Subject ID numbers and their cell phone numbers or email addresses are entered into the system to allow subjects to receive messages and send responses to the study database. The company adheres to a strict privacy policy for phone numbers in the system, which is detailed in section 1.3.10. In the daily text or email message, subjects are asked to classify their bleeding using the terminology recommended by Mishell et al (32). This includes for a given 24-hour period whether the woman has experienced:

1. Bleeding – any day during which bleeding requires the use of protection with a tampon, pad or panty liner.
2. Spotting – Minimal blood loss that does not require the use of any protection including panty liners (Use of precautionary liners does not qualify as spotting).
3. No bleeding

A second message will be sent one minute after the first to inquire whether subjects took the study medication that day. If the subject does not respond to the text or email messages, a second set of texts or emails (2) will be sent the following morning. The subject has only these two chances to report their bleeding information for that day, and otherwise must use the paper diary. Responses to the messaging system will be compiled in a secured web database by Mir3, which can be accessed by research staff for data retrieval and entry onto research computers. Paper diaries will also be provided for use in case of technical difficulty in receiving or responding to text or email messages. Subjects are encouraged to complete paper diaries in addition to the electronic diary.

Follow up visits

Thirty days after initiating study drug, participants will receive an email with a link to a final study online survey via REDCap (attached). This survey will include questions assessing side effects, adverse events, and bleeding and IUS satisfaction. The satisfaction questions will utilize an electronic 100-mm visual analog scale. This study survey should take approximately 5-10 minutes to complete. Subjects not returning the survey within 7 days will be contacted by phone, text or email (based on stated contact preferences) and reminded to reply.

Compensation

Subjects will be compensated \$10 at enrollment and \$30 at the first study visit, which totals \$40. Additionally, subjects will be provided with compensation for completing the electronic bleeding diaries after use of study drug. Subjects will receive an additional \$1 each day that they respond to the electronic messages (up to 30 days total) and \$20 for completing the final survey. This is a total of up to \$50 that they can earn from completing the diaries and completing the study. The total compensation per subject is a maximum of \$90. Compensation will be loaded onto a debit card, which participants will receive at the enrolment visit.

1.3.8 Risks and Benefits to Participants

Risks and discomforts

Risks to subjects include experiencing side effects from tamoxifen. The most common side effects reported with long term use are hot flushes (33%), bone pain (6%), gastrointestinal distress (5%), or fatigue (4%) (31). Risks of endometrial pathology including endometrial hyperplasia have been associated with long-term use of tamoxifen, but not with short-term use (31). Other risks of long-term use include increased risk of blood clots and stroke. Among women who developed pulmonary emboli, diagnosis occurred at a mean of 27 months from onset of tamoxifen treatment, with earliest event reported at 2 months of treatment (31). Women

using tamoxifen may be at increased risk for developing ovarian cysts with long-term use, but these resolve after discontinuation of use. Given that participants will only be using tamoxifen for one week in this study, an increase in severe adverse events is not anticipated. In short term use, the most common side effect reported was headache in up to 20% of women.

Women with a contraindication to tamoxifen use will be excluded from this study. This includes pregnant women given concern for teratogenicity. It is not known if tamoxifen is excreted in breast milk, but it has been shown to inhibit lactation. It has also been shown to cause reproductive tract lesions in exposed neonatal rodents (31), thus lactating women will also be excluded. Women regularly taking medications that interact with tamoxifen will also be excluded as described in section 1.3.3.

Other risks to participants include time spent participating in study without guarantee of benefit. It is estimated that daily time spent on participation will be no more than five minutes per day, in addition to the 15-minute study visit and the 5-10 minutes for the completion survey. Despite little time required for participation, this may be seen as an inconvenience to subjects.

There is a small risk of breach of confidentiality with potential risk disclosure of sensitive information including menstrual, sexual, and obstetric histories. Information discussed may be seen by participants as embarrassing or very personal. They will have a right to refuse disclosure of any questions they do not wish to discuss.

Benefits:

Participants may or may not personally benefit from being in this study. There is a possibility the study drug will improve participants' bleeding patterns and satisfaction with their LNG-IUS.

